6.5 POOLING OF CENTRES

This section is not applicable.

6.6 HANDLING OF MISSING DATA AND OUTLIERS

Missing or incomplete AE dates are imputed according to BI standards (3). Missing efficacy data, including vital status, tumour imaging data, will not be imputed in general. All reasonable efforts have been undertaken during the study to obtain such data.

Missing or incomplete drug stop dates are imputed as follows:

- If month and year known for drug stop date but day missing, then use date of death if within the month; otherwise use last day of month.
- If both month and day unknown, then use the first available date in this order: date of death, date of last contact, last day of the month of last visit.

Missing data and outliers of PK data are handled according to (2). Samples marked as no sample available (NOS) or non-valid result (NOR) will not be included in the analysis. Please refer to Sections 7.3.5 and 7.4 of the CTP for more details.

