Informed consent /patient assent	x ⁵											
Demographics	x											
Medical history	x											
Physical examination including neurological exam in patients with brain tumours	x	x	x	x	x	x	x	x	x	x		
Ophthalmologic examination	x									x		
Pulmonary examination ⁶	x	x					x		x	x		
Performance score ²²	x	x					x		x	x		
Vital signs	x	x	x	x	x	x	x	x	x	x		
Height ⁷	x								x ⁷			
Weight	x	x		x	x	x	x	x	x			
Safety laboratory tests ⁸⁻⁹	x	x ⁸		x ⁹	x ⁹	x ⁹	x	x ⁹	x	x ⁸		
Pregnancy test (if appl.) ¹⁰	x									x		
12 lead-ECG ¹¹	x			x					x ¹¹	x		
LVEF echo	x						x		x ¹²	x		
Disease assessment imaging ¹³	x								x ¹³	x		
Tumour marker(s) ¹⁴	x						x		x	x		
Tumour sample tissue availability ²³	x											
Review in-/ex- criteria	x											
Dose assessment	x						x ¹⁵	x ¹⁵	x ¹⁵			
Dispense trial drug ¹⁶		x					x		x			
Afatinib administration		Continuous oral once daily, fasted										
Pharmacokinetics		x ¹⁷	x ¹⁷	x ¹⁷	x ¹⁷							
Adverse events	x	x		x	x	x	x ¹⁸	x	x	x	x	x ¹⁹
Concomitant therapies	x	x		x	x	x	x	x	x	x	x	
Compliance check				x			x		x	x		
Patient diary check			x	x	x	x	x		x	x		
Eligibility for treatment continuation							x		x			
Conclusion of treatment										x		
Conclusion of patient participation											x	
Survival status												x

- All courses are of 4 weeks duration (28 days). Day 1 of a new course should take place on day 29. Patients may continue on treatment for unlimited courses until the criteria for stopping medication are met (see [Section 3.3.4](#)). Visits are performed weekly for the first course. At course 2, visits will take place every 2 weeks ([Visit 2 day 8](#) and visit 4 day 22 are no longer requested). From course 3 onwards, only visits “1” are required.
- EOT= end of treatment – When the decision is taken to permanently discontinue the study medication, the EOT visit must be performed within 7 days after last administration of afatinib. If the decision is taken at a scheduled visit, the EOT visit will be performed instead of the scheduled visit. Examinations performed at this time may need to be renamed for the actual visit conducted.
- FU= safety follow-up 28 to 30days after last afatinib administration. With the FU visit the patient will have completed his/her trial participation.
- OP= observation (post-trial) period. Collection of information on vital status every 3 months. Information could be collected from the patient’s notes or by telephone contact. A formal visit is not required.

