6. GENERAL ANALYSIS DEFINITIONS

6.1 TREATMENT(S)

Daily single oral doses of afatinib will be investigated in this study for paediatric patients. Dose escalation starts at 80% of the adult MTD by m^2 BSA and allometric scaling (Level 0) and can be escalated to 100% (level 1), 125% (level 2) and 150% (level 3) of the adult dose if required. In case level 0 exceeds the MTD, a dose level -1 will allow de-escalation to 50% of the adult MTD dose by m^2 BSA and allometric scaling. Oral solution is available for younger children and patients who cannot swallow afatinib film coated tablets.

Analysing treatment periods are defined in Table 6.1: 1 for reporting of treatment emergent AEs and safety laboratory data. An adverse event will be assigned to the analysing period where start date \leq onset date of AE < stop date.

Table 6.1: 1 Definition of analysing treatment periods

Analysing treatment period	Start date (including)	Stop date (excluding)
Screening	Date of informed consent	Date of first intake of study drug
Course 1	Date of first intake of study drug	Start date of Course 2, or date of first intake of study drug + 28 days if the patient did not start Course 2
On-treatment	Date of first intake of study drug	Date of last intake of study drug + 29 days
Residual effect period (REP)	Date of last intake of study drug + 1 day	Date of last intake of study drug + 29 day
Off-treatment	Date of last intake of study drug + 29 day	Date of last follow up visit + 1 day or date of death + 1 day whichever occurred first

The residual effect period (REP) for afatinib is 28 days after last intake of afatinib. Data recorded between the first study drug intake until up to 28 days after the last study drug intake will be considered as on-treatment.

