7.8.1 Adverse events

The analyses of adverse events (AE) will be descriptive in nature. All analyses of AEs will be based on the number of patients with AEs and not on the number of AEs. For analysis of duration, severity etc. of multiple AE occurrences, data on the case report form (CRF) will be collapsed into AE episodes provided that all of the following applies:

- The same MedDRA lowest level term was reported for the occurrences.
- The occurrences were time-overlapping or time-adjacent (time-adjacency of two occurrences is given if the second occurrence started on the same day or on the day after the end of the first occurrence).
- Treatment did not change between the onset of the occurrences or treatment changed between the onsets of the occurrences, but no deterioration was observed for the later occurrence.

For further details on summarization of AE data, please refer to the BI guideline (4).

The analyses of adverse events will be based on the concept of treatment-emergent adverse events. That means that all adverse events occurring between first drug intake and 28 days after last drug intake or death, whichever occurs first, will be assigned to the on-treatment period. All adverse events occurring before any study drug intake will be assigned to 'screening' and all adverse events occurring after last study drug intake + 28 days will be assigned to 'Off-treatment' (for listings only). For details on the treatment definition, see [Section 6.1](#).

An overall summary of adverse events will be presented. The frequency of patients with adverse events will be summarised by highest CTC grade (grades 1, 2, 3, 4, 5 and all grades), treatment, primary system organ class and preferred term for each of the following AE tables as well as relatedness of AEs to treatment and seriousness:

- DLTs (1st course and all courses)
- All AEs
- Drug-related AEs
- AEs leading to dose reduction
- AEs leading to treatment discontinuation
- Drug-related AEs leading to dose reduction
- Drug-related AEs leading to treatment discontinuation
- AEs leading to death
- Serious AEs
- Drug related serious AEs
- Other significant AEs, defined as AEs leading to dose reduction or permanent discontinuation of study medication
- Non-serious AEs with higher than 5% occurrence rate for disclosure on ClinicalTrials.gov

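### SAP 6.6 imputes a drug stop date with unknown month and day from death or last contact without an upper bound, which can stretch the on-treatment window well past the true stop

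*SAP*

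**What the plan says.** SAP 6.6 has two rules for an incomplete drug stop date.

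- Month and year known, day missing: "then use date of death if within the month; otherwise use last day of month".
- Month and day both unknown: "then use the first available date in this order: date of death, date of last contact, last day of the month of last visit".

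The stop date then sets the safety windows. SAP 6.1 states: "The residual effect period (REP) for afatinib is 28 days after last intake of afatinib". Table 6.1:1 ends the on-treatment period, exclusive, at "Date of last intake of study drug + 29 days". It ends the off-treatment period at "Date of last follow up visit + 1 day or date of death + 1 day whichever occurred first". SAP 7.8.1 takes events "between first drug intake and 28 days after last drug intake or death, whichever occurs first, will be assigned to the on-treatment period", and "all adverse events occurring after last study drug intake + 28 days will be assigned to 'Off-treatment' (for listings only"). SAP 7.8.2 applies the same window to laboratory values. SAP 7.7 summarises exposure mainly as total on-treatment time.

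Protocol 7.3.3 likewise says that later events are in general attributed to the post-study period and shown apart from on-treatment events. It leaves room for an additional combined table.

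On timing, the protocol flow chart notes say that "the EOT visit must be performed within 7 days after last administration of afatinib" and place the safety FU visit 28 to 30 days after the last dose. Protocol 6.1 and 6.2.4 then have sites collect vital status every 12 weeks (the flow chart says every 3 months; I use 12 weeks).

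**The concern.** The two rules do not match. The first keeps the imputed date inside the known month and uses death only if it falls there. The second has no such limit. A recorded death takes precedence over everything else, however late it is, and the EOT visit is not in the list at all. If only the year of the stop is known, the rule can still return a date in a later year.

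Death and last contact can come long after treatment, because patients enter an observation period with no fixed end. Protocol 3.3.4.1 says that relevant (S)AEs and further anti-cancer treatment are still recorded in that period. A stretched window can therefore take in events that arose after the drug was stopped, possibly under another therapy, and show them in the on-treatment tables.

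**Working it through.** **Inputs.** Windows from SAP Table 6.1:1 and 7.8.1; EOT and FU timing from the protocol flow chart notes; contact interval from protocol 6.1 and 6.2.4 (12 × 7 = 84 days); planned numbers from the protocol synopsis (17 + 38 = 55). I take the drug in SAP 6.6 to be the study drug; the text does not say so.

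**1. The plan's own figure.** The residual effect period runs from last intake + 1 (included) to last intake + 29 (excluded): 29 − 1 = 28 days, as stated.

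**2. The known-month rule.** Worst case, the drug is stopped on the 1st of a 31-day month and imputed to the 31st: 30 days late.

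**3. The unknown-month rule.** Set the true stop to day 0, so the window should end on day 28. With F the day of the FU visit (28 to 30) and k later contacts, imputed stop = F + 84k and window end = F + 84k + 28.

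| Date used | Days late | Window ends on day |
|---|---|---|
| FU visit (k = 0) | 28 to 30 | 56 to 58 |
| First later contact (k = 1) | 112 to 114 | 140 to 142 |
| Second later contact (k = 2) | 196 to 198 | 224 to 226 |
| Death on day D | D, no limit | D (SAP 7.8.1 stops at death) |

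**4. When death is used.** The off-treatment period starts at D + 29 and ends no later than D + 1. It ends at least 28 days before it starts, so it is empty. Every event reported from the first dose to death is then on-treatment.

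A side point: if the last follow-up visit in Table 6.1:1 means the safety FU visit, the off-treatment period lasts only 0 to 2 days even with a correct stop date (28 + 1 − 29 = 0; 30 + 1 − 29 = 2), whereas SAP 7.8.1 sets no end. The two should be reconciled.

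**5. Other anchors.** An EOT visit on schedule is at most 7 days late. A year limit alone is weak: 1 January to 31 December of a non-leap year is 364 days.

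**6. Which events can move.** Only events after day 28 that were reported. If last contact is the FU visit, that is essentially days 29 and 30. If it is the first later contact, it is days 29 to 112–114. After FU, protocol 5.2.2.2 asks for SAEs and AESIs only if the investigator considers them relevant.

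**7. Effect on a rate.** SAP 7.8.1 counts patients, so one patient adds at most 1/55 = 1.8 points overall or 1/38 = 2.6 points in the expansion part. The patient must not already be counted in that category. Tables with fewer patients have larger steps.

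**The case against.** The trigger should be rare. Both month and day must be missing despite a dose diary, a check of returned drug after each course, accountability records and the EOT visit. A patient whose stop month is unknown may well have missed the EOT visit, and the alternative then falls back on much the same dates. In a first-in-child trial, erring towards on-treatment is a defensible caution, and protocol 7.3.3 allows post-study events to be combined with on-treatment events. The SAP does not define last contact, so it may simply be the FU visit. The exposure definition is referred to TSAP 5.4, which is not in the public text.

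Much of this stands and limits the size. Caution does not, however, justify a stop date later than a recorded EOT visit or outside the recorded year, and a longer exposure time is not cautious.

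A reader might infer more: that late disease events and deaths are attributed to the drug, or that every affected patient shifts the rates. The documents do not support this. Protocol 5.2.2.1 exempts progression, including death from it, from (S)AE reporting unless a causal link to the drug is suspected. It also has the investigator judge causality separately, and SAP 7.8.1 tabulates drug-related events separately. On-treatment is a time window, and most affected patients would have no event to move.

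**Conclusion.** The point holds as a small defect in a stated rule. When month and day are unknown, the imputed stop can be 28 to 30 days late (FU visit), 112 to 114 days late (first later contact) or late without limit (death). The on-treatment window grows accordingly. Exposure time probably grows too, but that cannot be confirmed without TSAP 5.4. With death as the stop, no off-treatment period is left, contrary to the general separation in protocol 7.3.3.

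The ceiling per affected patient is 1.8 points (1/55) or 2.6 points (1/38) in a descriptive rate, reached only when a relevant event was reported late. The documents give no count of affected patients; I assume few. Causality assessments are untouched. So are the primary endpoints: DLT is assessed in the first 28 days and objective response does not use the stop date.

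**What to change.** In SAP 6.6, replace the priority order for unknown month and day with the earliest available of:

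- EOT visit date,
- date of death,
- date of last contact (to be defined),
- 31 December of the stop year, when the year is known,

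but never earlier than the last documented intake. Keep the last day of the month of the last visit only as the final fallback. List every patient with an imputed stop date.

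I would not cap the date by the supply dispensed: pauses and missed doses can make leftover drug last longer, so such a cap could precede the true last dose.

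The cost is one sentence, one derivation and a short listing, all from dates already scheduled for collection. The small downside is that, if an EOT visit is mistimed, a few late events could move to the off-treatment listings.

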6.7 BASELINE, TIME WINDOWS AND CALCULATED VISITS

Study days and visits will be labelled according to the flow chart of the CTP.

Unless otherwise specified, baseline is defined as the latest time point before the very first administration of any study medication. If this criterion is not fulfilled, then no baseline will be derived. Note that for some trial procedures (for example performance score, body weight, vital signs, laboratory tests) this may be the value measured on the same day when trial medication was started. In these cases it will be assumed that the measurements were taken prior to the intake of any study medication. For laboratory values where not only the examination date but also time are recorded, examination time has to be taken into account when defining baseline. That is, a laboratory value on the same date as the first study drug administration is considered as baseline value if and only if the time of laboratory value is before or the same as the time of first study drug administration. If any of these times are missing and the date of laboratory value is equal to the date of first study drug administration, then the laboratory assessment will be considered as according to protocol, i.e. as prior to first study medication.

7. PLANNED ANALYSIS

For End-Of-Text (EoT) tables, the set of summary statistics is: N / Mean / SD / Min / Q1 (lower quartile) / Median / Q3 (upper quartile) / Max.

Tabulations of frequencies for categorical data will include all possible categories and will display the number of observations in a category as well as the percentage (%) relative to the respective treatment group (unless otherwise specified, all patients in the respective patient set whether they have non-missing values or not). Percentages will be rounded to one decimal place. The category missing will be displayed only if there are actually missing values.

7.1 DEMOGRAPHIC AND OTHER BASELINE CHARACTERISTICS

Only descriptive statistics are planned for this section of the report.

7.2 CONCOMITANT DISEASES AND MEDICATION

Only descriptive statistics are planned for this section of the report.

7.3 TREATMENT COMPLIANCE

Only descriptive statistics are planned for this section of the report.

7.4 PRIMARY ENDPOINT(S)

7.4.1 Dose Finding Part:

One of the primary objectives is to assess the MTD based on the number of patients presenting DLTs during the MTD evaluation period. Therefore, an overall summary of DLTs (see CTP Section 4, Table 4.1.4.1.2 for the definition of DLTs) which occurred during the MTD evaluation period will be provided for each dose cohort from the dose finding cohort treated set. Patients who were replaced within the MTD evaluation period will be excluded from the determination of the MTD but will be considered for all other safety evaluations.

A summary of the number of patients with DLTs overall in any course will be also given by initial treatment and displayed in a similar format to the summary of DLTs occurring in the MTD evaluation period.

The determination of the MTD is based on a Rolling 6 design as illustrated in Section 4, Table 4.1.4.1:1 of the CTP. The MTD is defined as the highest dose at which no more than 1/6 patients experienced DLT considered related to afatinib during the MTD evaluation period. Refer to CTP 7.3.1 for further details on MTD evaluation.

Analysis of the standard PK endpoints is performed according to (2) and (8) as outlined in Section 7.3.5 of the CTP.

7.4.2 MTD expansion cohort part:

Objective response (OR) is defined as a best overall response of complete response (CR) or partial response (PR) based on investigator's assessment according to the institutional

response evaluation criteria for the given tumour type. If the International Criteria for Neuroblastoma Response Criteria (INRC) is used, OR is defined as complete response (CR), very good partial response (VGPR), partial response (PR) and mixed response (MxR). For further details on OR, please refer to CTP Section 7.3.1. The objective response rate will be calculated and reported as proportion of responders with 95% Clopper-Pearson CIs based on all treated patients. Objective response will be summarized regardless of confirmation.

Additional summary or listing may be provided for confirmed response. If only few patients (fewer than 5) achieved objective response, a detailed listing will be reported.

For objective responses, evaluated by institutional response evaluation criteria other than INRC, below confirmation rule for best overall response will be considered.

- If CR or PR: look at all subsequent visits, if there is another CR or PR ≥ 28 days then the patient has a confirmed response. If there is not another CR or PR ≥ 28 days then the patient can be SD. Please note that once patient achieve CR any response other than CR will be considered as PD.

Detailed specifications are listed in Table 7.4.2: 1.

Table 7.4.2: 1 Confirmation rule for best overall response

Overall response (time point 1)	Overall response (subsequent time point)	Unconfirmed best overall response	Confirmed best overall response
CR	CR (≥ 28 days from 1)	CR	CR
CR	CR (< 28 days from 1)	CR	SD
CR	PR ¹	CR	SD
CR	SD	CR	SD
CR	PD	CR	SD
CR	NE/Missing	CR	SD
PR	CR (≥ 28 days from 1)	CR	PR
PR	CR (< 28 days from 1)	CR	SD
PR	PR (≥ 28 days from 1)	PR	PR
PR	PR (< 28 days from 1)	PR	SD
PR	SD	PR	SD
PR	PD	PR	SD
PR	NE/Missing	PR	SD

¹= If truly a CR at first response, any subsequent disease (even a PR relative to baseline) makes the disease PD. Could only be a PR if initial CR is changed to PR (i.e. not a true CR).

For INRC, a similar derivation of confirmed response will apply. That is, a subsequent assessment with the same or a better overall response on or after 28 days is required for the confirmation of an objective response, in the order from best to worst of CR > VGPR > PR > MxR. Otherwise, a SD will be considered as the confirmed best overall response.

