For all patients, the reason for withdrawal (e.g. adverse events) must be recorded in the eCRF. These data will be included in the trial database and reported.

If the patient and/or parents and/or legal guardian withdraw assent/consent to continue further trial procedures and the follow-up visit activities, no additional study assessments will be completed. In this event patients and parents or legal guardians will be asked whether they agree to allow continued further data collection of associated clinical outcome parameters during the observation period. If the patient/parents do not permit further contact/data collection this will be documented in the eCRF and in the source data.

Patients who withdraw from the trial after entering active treatment phase may be replaced if the primary endpoint of the respective trial phase is not achieved (see [Section 5](#)).

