During the first course of the dose finding part, patients should not miss more than 25% of afatinib doses (regardless of the reason of missed doses) to render patients evaluable for MTD. For details, see [section 7.3](#).

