5. ENDPOINT(S)

5.1 PRIMARY ENDPOINT(S)

Dose finding part:

- The primary endpoint is the **dose limiting toxicity** (DLT) measured during the first course of treatment. DLTs are defined in Table 4.1.4.1.2 of the CTP.
- **Pharmacokinetics** ($AUC_{\tau,ss}$, $C_{max,ss}$)

The primary objective of the dose finding part is to determine the maximum tolerated dose (MTD) of the study drug as defined by patients with DLT in a paediatric population. The MTD will be determined as the highest dose at which no more than 1/6 patients experienced DLT. The MTD evaluation period is defined as the initial 28 days of study treatment. Patients who developed DLT at any time during the initial 28 treatment days and patients who have completed the MTD evaluation period without missing more than 25% of the afatinib doses regardless of the reason will be referred to as patients evaluable for DLT.

MTD expansion cohort part:

- **Objective response** (OR) by investigator assessment according to the institutional response evaluation criteria for the given tumour type, assessed every 8 weeks until progression of disease.

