6.3 PATIENT SETS ANALYSED

Treated set (TS):

This patient set includes all patients enrolled in the trial who were documented to have taken at least one dose of study medication.

Dose finding cohort treated set:

This patient set includes all patients enrolled in dose finding cohort of the trial who were documented to have taken at least one dose of study medication.

MTD Expansion cohort treated set:

This patient set includes all patients enrolled in expansion cohort who must satisfy the following criterion:

- Patients' tumour must be tested for positivity on 2 of the following tests: EGFR IHC>150 and/or HER2 IHC>0 and/or EGFR FISH positive and/or HER2 DDISH positive.

or

- Patient will have proven genomic, transcriptomic or proteomic alterations which are not defined above.

and

- Patients who were documented to have taken at least one dose of study medication.

PK analysis set (PKS):

This set includes all patients in the treated set (TS) who provided at least one PK endpoint that was not excluded due to a protocol deviation relevant to the evaluation of PK or due to PK non-evaluability. Thus, a patient will be included in the PKS, even if he/she contributes only one PK parameter value for one period to the statistical assessment. Descriptive and model based analyses of PK parameters will be based on the PKS.

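### SAP 7.4.1 reports the primary DLT summary on the treated set rather than on the DLT-evaluable patients defined in SAP 5.1, so the reported DLT rate can be diluted

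*SAP*

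**What the plan says.** Four parts of the SAP meet here.

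- **SAP 5.1** sets the MTD evaluation period at the first 28 days of treatment. Two groups "will be referred to as patients evaluable for DLT": those with a DLT at any time in that period, and "patients who have completed the MTD evaluation period without missing more than 25% of the afatinib doses regardless of the reason".
- **SAP 6.3** lists the analysis sets. None is defined by DLT evaluability. The set for this part is broad: "This patient set includes all patients enrolled in dose finding cohort of the trial who were documented to have taken at least one dose".
- **SAP 7.4.1** says that the DLT summary for the MTD evaluation period "will be provided for each dose cohort from the dose finding cohort treated set". The next sentence deals with the MTD count: "Patients who were replaced within the MTD evaluation period will be excluded from the determination of the MTD". Those patients stay in the other safety evaluations.
- **SAP 7** gives the default base for percentages: "all patients in the respective patient set whether they have non-missing values or not".

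Protocol 4.3 carries the same dosing limit for the first course: "patients should not miss more than 25% of afatinib doses (regardless of the reason of missed doses) to render patients evaluable for MTD". Protocol 3.3.4.1 says that patients who withdraw after starting treatment "may be replaced if the primary endpoint of the respective trial phase is not achieved".

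**The concern.** A patient who leaves early without a DLT, or who misses a third of the doses, says little about whether a dose is tolerable over 28 days. Both documents therefore define evaluability, and the MTD rule is a statement about evaluable patients. The table that reports the primary safety endpoint does not use that definition. If a dose level contains non-evaluable patients, the table shows a lower DLT rate than the one behind the MTD decision, and a reader cannot trace the decision from the table.

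A second, smaller gap is the trigger for exclusion. SAP 7.4.1 removes patients who were replaced. Under protocol 3.3.4.1 replacement is optional and is written for withdrawals. A patient who stays on trial, has no DLT and misses more than 25% of doses is not evaluable under SAP 5.1, yet SAP 7.4.1 does not expressly exclude that patient. The cross-references do not settle it:

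- Protocol 4.3 points to protocol 7.3, which defines only the treated set.
- SAP 7.4.1 points to protocol 7.3.1, which refers simply to patients in the dose finding part.
- Protocol Table 4.1.4.1:1 notes that it leaves unevaluable patients out of account.

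**Working it through.** **1. The plan's own figures.** Protocol 7.6 estimates 24 evaluable patients and 30 recruited. Four levels (0 to 3) × 6 = 24. Setting 24/(1 − d) = 30 gives d = 1 − 24/30 = 0.20. The 20% is implied, not stated, but it shows that non-evaluable patients were expected. (Protocol 7.1 describes the 30 as evaluable; 7.6 is followed here, and the two should be reconciled.)

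**2. Direction.** At one dose level let n be the evaluable patients, x those with a DLT in the 28 days, and k the treated but non-evaluable patients. By SAP 5.1 every patient with such a DLT is evaluable, so the k patients contribute no DLT. The table shows x/(n + k) instead of x/n. The ratio of the two is n/(n + k), which is never above 1.

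**3. Size, with n = 6.**

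| k | One DLT | Two DLTs |
|---|---|---|
| 0 | 1/6 = 16.7% | 2/6 = 33.3% |
| 1 | 1/7 = 14.3% | 2/7 = 28.6% |
| 2 | 1/8 = 12.5% | 2/8 = 25.0% |
| 3 | 1/9 = 11.1% | 2/9 = 22.2% |

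At the implied 20%, six evaluable patients correspond to 6/0.80 = 7.5 treated, so k of one or two per full level is what the planning figures suggest.

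**4. Against the 1/6 threshold.** Two DLTs would display at or below 1/6 only if 2/(6 + k) ≤ 1/6, that is, k ≥ 6. No row of the table reaches this.

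**5. What the documents say about k.** Protocol 7.6 gives 17 patients in the dose finding part. The rolling six design allows up to six per level. If only levels 0 and 1 were opened, at most 12 could be evaluable, and 17 − 12 = 5 would not be. If level 2 was also opened, 18 places were available and k could be zero. The documents do not say which levels were opened. Protocol 3.3 speaks of 55 patients evaluable for MTD or OR, and 17 + 38 = 55, so the planning text counts all 17 as evaluable.

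**6. Timing.** Protocol 4.1.3 and 7.6 report the MTD as already determined. The interim report cited there is dated 21 June 2016. The first final SAP is dated 17 January 2018 (SAP history table).

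**The case against.** The strongest reply has three parts.

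- **The treated set follows the protocol.** Protocol 7.3 puts everyone with a dose into the safety analysis, 7.3.3 tabulates DLTs by dose cohort with no evaluability limit, and SAP 7.8 runs safety on the treated set.
- **The MTD is protected elsewhere.** SAP 5.1 gives the 1/6 rule and the definition of evaluability together. Protocol 4.3 makes the 25% limit a condition whether or not the patient withdraws. Protocol 4.1.2 recruits until patients are evaluable for MTD, 4.1.4.1 fixes the MTD once the last patient is evaluable, and 7.1 counts evaluable patients. SAP 7.4.1 removes replaced patients.
- **The table is descriptive.** No hypothesis is tested. Because the summary is introduced as serving the MTD assessment, it could be read as already leaving out replaced patients.

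The second part stands, and it confines this point to reporting. The first does not remove the mismatch. SAP 7.8.1 already lists DLTs for the first course and for all courses on the treated set, so the 7.4.1 summary need not repeat that view. Its stated purpose is the MTD, so its base should be the MTD base. The generous reading in the third part is not what is written: the exclusion is stated for the determination of the MTD, while the summary is assigned to the full treated set.

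**Conclusion.** The mismatch between SAP 5.1 and SAP 7.4.1 is real, and its effect can go only one way. At a level with six evaluable patients, one non-evaluable patient takes about 5 percentage points off a rate of 2/6 (33.3% to 28.6%) and about 2 points off 1/6 (16.7% to 14.3%). Whether any dilution occurs depends on the number of non-evaluable patients, which the documents do not give. The six-patient level and the one to three extra patients are illustrations.

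A reader might infer three stronger things that the documents do not support.

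- **That non-evaluable patients count as DLT-free in the 1/6 rule, so the MTD is in doubt.** The provisions listed under the objection tie the MTD to evaluable patients, and the MTD was set before the SAP was final. What remains is a loose trigger word in SAP 7.4.1.
- **That at least 5 of the 17 patients were non-evaluable.** This assumes that only two levels were opened, which is stated nowhere. The number could be zero.
- **That the table will understate toxicity.** It can do so, but only at a level with at least one non-evaluable patient.

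The point should be corrected because it concerns a primary endpoint and the change is small. It does not reopen the dose decision.

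**What to change.** - Add a DLT-evaluable set to SAP 6.3, using the SAP 5.1 definition unchanged.
- Base the SAP 7.4.1 summary for the MTD evaluation period on that set, and show the treated number beside the evaluable number for each dose cohort.
- In SAP 7.4.1, replace the exclusion of patients replaced within the MTD evaluation period by an exclusion of patients not evaluable for DLT as defined in SAP 5.1.
- Keep the treated set for all other safety tables, including the DLT tables in SAP 7.8.1.

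The cost is SAP wording and one derived flag. DLT percentages may become slightly less favourable. If every treated patient turns out to be evaluable, nothing changes, and the two numbers side by side will show that.
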